5.7 Replacement of Subjects

During the Phase 1 portion of the study, subjects will be replaced for any of the following:

- Missed any doses of pralatrexate during the DLT period (not due to DLT).
- Did not receive the doses of pembrolizumab during the DLT period (not due to DLT).

Subjects who are replaced for missed doses may continue to receive study treatment if there is clear clinical benefit, but will not be included in DLT analysis.

During the Phase 2 portion of the study, subjects who did not receive at least 1 dose of pembrolizumab and 1 dose of pralatrexate, or who did not have a tumor response assessment (except due to progression of disease prior to the first tumor response assessment) will be replaced. If a patient discontinues study treatment prior to the first response assessment due to progressive disease, the treating physician is encouraged to obtain imaging to confirm progression.

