During the Phase 1 portion of the study, a modified, more conservative version of the Rolling 6 design of Skolnik et al will be employed. In this design, at most, 3 patients will be under observation for DLT on the current test dose level at any time. DLT observation period is 2 cycles. Patients who did not receive the doses of pembrolizumab during DLT period (not due to DLT), or those who missed any doses of pralatrexate during DLT period (not due to DLT) will be replaced. Once 3 patients are evaluable with no patient at that dose level experiencing a DLT, the dose can be escalated, or up to 3 additional patients may be treated at the current dose level. No more than 6 evaluable patients will be accrued to any dose level. Escalation will terminate as soon as \geq 2 patients experience DLT at a given dose level. If 1/6 patients experience DLT at the current dose level, the dose will be escalated to the next higher level. If more than 1/6 patients experience DLT, then the next lower dose will be expanded. MTD will be declared the highest dose level at which 6 evaluable patients have been treated and, at most, 1/6 patients experiences DLT. The MTD will be considered the RP2D, unless the PI chooses a lower dose level, based on toxicity in subsequent cycles.

Phase 2 portion

In the phase 2 portion, patients will be treated at the RP2D. The phase 2 portion of this study will implement a Gehan two-stage design to estimate the ORR and to evaluate the activity of the combined regimen. Patients treated during the Phase 1 portion at the RP2D will be included in the Phase 2 evaluations if they are evaluable for response, defined as patients who received at least 1 dose of pembrolizumab and at least 1 dose of pralatrexate and had at least 1 disease assessment. The sample size is based on the desire to estimate the response rate with approximately 10% standard error, and early stopping if the combination is unexpectedly ineffective. In the pivotal PROPEL trial, the overall response rate (ORR) in 109 evaluable patients who received pralatrexate as a single agent was 29%, including 12 (11%) complete responses (CR) and 20 (18%) partial responses (PR).⁵

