12.1.1 Phase 1 design

During the Phase 1 portion of the study, a modified, more conservative version of the Rolling 6 design of Skolnik et al will be employed.⁸⁷ In this design, at most, 3 patients will be under observation for DLT on the current test dose level at any time. DLT observation period is 2 cycles (defined in [Section 5.5](#)). DLTs are defined in [Section 5.5](#). Patients who are not evaluable for DLT (defined in [Section 5.7](#)), i.e., those who did not receive the doses of pembrolizumab during DLT period (not due to DLT) or those who missed any doses of pralatrexate during DLT period (not due to DLT), will be replaced. Once 3 patients are evaluable

with no patient at that dose level experiencing a DLT, the dose can be escalated, or up to 3 additional patients may be treated at the current dose level. No more than 6 evaluable patients will be accrued to any dose level. Escalation will terminate as soon as ≥ 2 patients experience DLT at a given dose level. If 1/6 patients experience DLT at the current dose level, the dose will be escalated to the next higher level. If more than 1/6 patients experience DLT, then the next lower dose will be expanded. MTD will be declared the highest dose level at which 6 evaluable patients have been treated and, at most, 1/6 patients experience DLT. The MTD will be considered the RP2D, unless the PI chooses a lower dose level, based on toxicity in subsequent cycles.

These rules are outlined in the Table below.

Table 12.1.1. Dose Escalation Rules

# Patients on Current Level			Action
With DLT [^]	Evaluable	Evaluable + At Risk [^]	
0	0	1-2	Accrue next patient at this level*
0	0	3	Hold accrual
0	1	1-3	Accrue next patient at this level
0	1	4	Hold accrual
0	2	2-4	Accrue next patient at this level
0	2	5	Hold accrual
0	3-6	3-6	Accrue next patient at the next higher level* ^{*,+}
1	1	1-2	Accrue next patient at this level
1	1	3	Hold Accrual
1	2	2	Accrue next patient at this level
1	2	3-4	Hold accrual
1	3-5	3-5	Accrue next patient at this level
1	3-5	6	Hold accrual
1	6	6	Accrue next patient at the next higher level*
2**	any	any	Accrue next patient at next lower level (max 6)

[^]: DLT: a patient with a documented DLT

Evaluable: a patient who is either fully evaluable for toxicity for the purpose of dose escalations or has a DLT

At Risk: a patient who is on treatment and has not yet passed the evaluation period nor had a DLT

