^{*}: During the dose-escalation portion, if higher dose level is already closed, the next lower dose will accrue to a total of 6 patients, with 2 or higher DLTs requiring further dose de-escalation.

⁺: Although under this scenario escalating to the next higher dose level is suggested, additional patients can be accrued to the current level -up to n=6 patients.

^{**}: Patients treated on a higher dose will have their treatment modified to the dose below the dose level with 2 DLTs, if pending patients have DLT.

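### Section 5.7 drops a patient whose DLT follows a pralatrexate dose missed for another reason; the Table 12.1.1 notes count that patient, so the two can reach opposite dose-level decisions

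*Combined protocol and SAP*

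**What the plan says.** **Replacement rule.** Section 5.7 replaces a phase 1 subject who misses any pralatrexate dose during the DLT period when the miss is not due to a DLT. Replaced subjects "may continue to receive study treatment if there is clear clinical benefit, but will not be included in DLT analysis". The synopsis repeats the trigger: "those who missed any doses of pralatrexate during DLT period (not due to DLT) will be replaced". So does the running text of Section 12.1.1, which introduces these subjects as "Patients who are not evaluable for DLT" and refers back to Section 5.7.

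**Table 12.1.1 notes.** These define the numerator as "DLT: a patient with a documented DLT" and an evaluable patient as "a patient who is either fully evaluable for toxicity for the purpose of dose escalations or has a DLT". Neither definition carries a dosing condition.

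**Decision rule.** Section 12.1.1 states: "MTD will be declared the highest dose level at which 6 evaluable patients have been treated and, at most, 1/6 patients experience DLT". Two DLTs at a level send the next patient to the next lower level. The table footnote applies the same limit when a lower level is expanded: "with 2 or higher DLTs requiring further dose de-escalation".

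**Observation window.** Section 5.5 runs the window from the start of Cycle 1 to the start of Cycle 3, including delays.

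**The concern.** A patient who misses a dose for a non-DLT reason and later has a different DLT is excluded by Section 5.7 but enters both numerator and denominator under the table notes. Section 12.1.1 is also split internally, since its text follows Section 5.7 and its table notes do not. Neither the synopsis nor Sections 5.5 and 5.6 say which reading governs.

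The case is foreseeable. Table 6.4.1 omits pralatrexate for grade 2 mucositis on a dosing day, and grade 2 mucositis is not a DLT under Section 5.5. A patient who omits Cycle 1 Day 8 still has the rest of the window in which another event can meet the DLT definition. Taken literally, Section 5.7 would drop even a later treatment-related grade 5 event.

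Establishing the MTD and RP2D is a primary objective, and the threshold is a single patient in six.

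**Working it through.** The plan states no operating characteristics for phase 1, so there is no figure of its own to reproduce.

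**Step 1. Decisions from the table rows.** Let X be a patient with a non-DLT miss followed by a separate DLT, with no other patients pending.

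| DLTs / evaluable among other patients | X counted (table notes) | X excluded (Section 5.7) |
|---|---|---|
| 0/3 | 1/4: stay at this level | 0/3: escalation allowed |
| 0/5 | 1/6: passes | 0/5, then 0/6 after a DLT-free replacement: passes |
| 1/2 | 2/3: next lower level | 1/2: continue at this level |
| 1/5 | 2/6: next lower level | 1/5, then 1/6 after a DLT-free replacement: passes |

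The verdicts are opposite when X would be the second DLT. They do not always differ, as the 0/5 row shows.

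**Step 2. Direction.** A patient who misses a dose and has no DLT is replaced under both readings. The only patients the table adds are therefore patients with a DLT. On the same stream of patients the table's count is never below the Section 5.7 count, so disagreement can only mean that Section 5.7 passes and the table fails.

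**Step 3. Size.** All inputs are assumptions except where a source is named.
- *p*, DLT risk in patients without an omission: 10%.
- *h*, DLT risk in patients with an omission: 10% or 20%.
- *o*, share omitting a dose for toxicity below the DLT threshold: 5%, 20.5% or 25%.
- The 20.5% comes from Section 2.3: 50% of patients had grade 1–2 mucositis and 41% of those had omissions or reductions, so 0.50 × 0.41 = 0.205. Adding grade 3–4 gives 0.205 + 0.21 × 0.23 = 0.253, close to the 25% row.

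DLT rate among counted patients:
- Section 5.7: *p*
- Table notes: (*o·h* + (1 − *o*)·*p*) / (*o·h* + 1 − *o*)

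Example with *o* = 0.205, *h* = 0.20: (0.041 + 0.0795) / (0.041 + 0.795) = 0.1205 / 0.836 = 0.144.

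P(at most 1 DLT in 6) at rate *q* is (1 − *q*)^6 + 6*q*(1 − *q*)^5. Under Section 5.7, with *q* = 0.10, it is 0.531 + 0.354 = 0.886. By Step 2, the probability of opposite verdicts is the difference between the two pass probabilities.

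| *o* | *h* | Rate, table | Pass, Section 5.7 | Pass, table | Opposite verdicts |
|---|---|---|---|---|---|
| 5% | 10% | 0.105 | 0.886 | 0.876 | 0.9% |
| 5% | 20% | 0.109 | 0.886 | 0.867 | 1.9% |
| 20.5% | 10% | 0.123 | 0.886 | 0.839 | 4.7% |
| 20.5% | 20% | 0.144 | 0.886 | 0.790 | 9.6% |
| 25% | 10% | 0.129 | 0.886 | 0.825 | 6.1% |
| 25% | 20% | 0.156 | 0.886 | 0.762 | 12.4% |

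An exact recursion over the patient stream gives the same six disagreement probabilities, with none in the reverse direction; 400,000 simulated streams agree.

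**Step 4. Sensitivity.** With equal risk in both groups, over 5% to 20.5% omission, disagreement is 0.3% to 1.6% at a 5% DLT risk and 2% to 10% at a 20% DLT risk.

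**The case against.** **The passages can be harmonised.** One could read the table's reference to having a DLT as the missing exception, or as merely mirroring the parenthesis in Section 5.7 for patients whose dosing was cut short by a DLT. Neither reading is written down. The parenthesis qualifies the reason for the missed dose, not what happens to the patient afterwards, and the table note has no dosing condition. Two defensible readings with different counts are the problem itself.

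**The commonest path is not affected.** If the mucositis behind the omission itself becomes the DLT, the miss can be read as due to DLT and both passages count it. This stands: the conflict is clear only for a different, later event.

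**The size leans high.** Much of this stands.
- The Section 2.3 figures are single-agent, cover the whole treatment, mix reductions with omissions and include grade 1 mucositis, for which Table 6.4.1 omits nothing. This trial also schedules leucovorin to reduce mucositis.
- Section 5.4 requires mucositis of at most grade 1 before a new cycle, so some events would delay Cycle 2 rather than cause a miss.
- Only the window after the omission matters. With a post-omission risk of 5% (an assumption), disagreement is 0.5%, 1.0% and 2.3% at omission shares of 5%, 10% and 20.5%.
- Section 5.7 lets replaced patients continue only with clear clinical benefit, and the first on-treatment staging is in Cycle 4, after the window.
- The 20% risk in omitters has no source in the documents.

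**Other safeguards exist.** Section 12.3.4 monitors all treated patients, Section 5.6 lets the principal investigator choose a lower RP2D, and the management team in Section 15.3 reviews enrolment. A second DLT would not go unseen. None of these provisions says whether it counts.

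**Conclusion.** The concern holds. Section 5.7, the synopsis and the Section 12.1.1 text say one thing, the Table 12.1.1 notes say another, and nothing ranks them. Followed literally, Section 5.7 removes real DLTs from the MTD decision, always in the direction of passing the dose.

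The contradiction rests on the wording alone; its size depends on assumptions. It is about 1 to 2 percentage points if 5% of patients omit a dose, and up to 9.6 or 12.4 points at omission shares of 20.5% or 25% with a 20% DLT risk in omitters. The 20.5% and 25% shares are best treated as upper anchors. The calculation assumes six patients evaluated per level, every later DLT a separate event, and every omitter staying on treatment, so true values could be lower. Larger values would need a much higher risk in omitters, for which the documents give no basis. It should be fixed, because who counts has to be settled before such a patient appears.

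**What to change.** State one rule for DLT evaluability and use it in all four places: the synopsis, Section 5.7, the running text of Section 12.1.1 and the notes to Table 12.1.1. The rule must say explicitly whether a documented DLT in the observation period counts regardless of earlier missed doses. The same sentence should cover pembrolizumab doses not received, where the wording has the same gap.

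The table's definition is already in the plan, and limiting replacement to patients without a DLT would bring the other passages into line with it. If the sponsor intends the Section 5.7 wording, the table notes need the matching change.

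The cost is a wording amendment. If the table's definition is kept, a dose is somewhat harder to declare the MTD: a pass probability of 76% to 88% instead of 89% in the scenarios above. That could move accrual from 30 toward the 36 evaluable patients that Section 12.2 already foresees, within the cap of 40.

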5.8 Agent Administration

5.8.1 Pembrolizumab

The Pharmacy Manual contains specific instructions for the preparation of the pembrolizumab infusion fluid and administration of infusion solution.

Pembrolizumab (200 mg) will be administered as a 30-minute IV infusion on Day 1 of each 21-day cycle.

The final concentration of the diluted solution should be 1 mg/mL - 10 mg/mL and administered IV over 30 minutes, through an intravenous line containing a sterile, non-pyrogenic, low-protein binding 0.2 micron to 5 micron in-line or add-on filter.

Every effort should be made to target infusion timing to be as close to 30 minutes as possible. However, given the variability of infusion pumps, a window of -5 minutes and +10 minutes is permitted (i.e., infusion time is 30 minutes: -5 min/+10 min).

The pembrolizumab dose is fixed at 200 mg. There are no dose reductions. Management and dose delays associated with pembrolizumab AEs are outlined in Section 6.3.

Pembrolizumab will always be given first (before pralatrexate).

5.8.2 Pralatrexate

Pralatrexate will be administered by intravenous (IV) push according to dose levels, over 3 to 5 minutes, via the side port of a free-flowing 0.9% sodium chloride injection on Days 1 and 8 of each cycle.

Pralatrexate dosing should be based on baseline body surface area (BSA). Patients with a BSA>2m² can be treated either at the actual BSA or at BSA=2m², at the Investigator's discretion. The patient will receive the same dose of pralatrexate (based on the BSA calculated at baseline) throughout treatment unless the patient's actual weight changes by $\geq 10\%$ (in that case the dose will be adjusted accordingly).

5.9 Assessments and Special Monitoring

[Section 10](#) summarizes the trial procedures to be performed. **Note:** Protocol therapy should be administered on Day 1 of each cycle after all procedures/safety assessments have been completed.

It may be necessary to perform study procedures at unscheduled time points if deemed clinically necessary by the investigator.

5.9.1 Special Monitoring for pembrolizumab.

Adverse events (both non-serious and serious) associated with pembrolizumab exposure may represent an immunologic etiology. These adverse events may occur shortly after the first dose or several months after the last dose of pembrolizumab.

Diarrhea/colitis

- Participants should be carefully monitored for signs and symptoms of enterocolitis (such as diarrhea, abdominal pain, blood or mucus in stool, with or without fever) and of bowel perforation (such as peritoneal signs and ileus).

Hyperthyroidism or hypothyroidism

- Thyroid disorders can occur at any time during treatment. Monitor patients for changes in thyroid function (at the start of treatment, periodically during treatment, and as indicated based on clinical evaluation) and for clinical signs and symptoms of thyroid disorders.

Management of infusion reactions

- Signs and symptoms usually develop during or shortly after drug infusion and generally resolve completely within 24 hours of completion of infusion.
- Appropriate resuscitation equipment should be available in the room and a physician readily available during the period of drug administration.

5.9.2 Monitoring for pralatrexate.

Oral mucositis is common and mucositis should be graded at each study visit. Oral mucositis will be graded according to the CTCAE v5.0 and pralatrexate dose delay/modification guidelines in section 6.4 should be adhered to.

5.10 Duration of Therapy and Criteria for Removal from Protocol Therapy

Participants will receive protocol therapy until one of the below criteria are met:

- Disease progression
- **Note:** Following consultation with the Study PI, participants who meet progression per 2014 Lugano classification⁸ but who meet the criteria of “indeterminate response” (IR) according to the provisional modification to the 2014 Lugano Classification, the LYRIC criteria¹⁰ ([Appendix C](#)), and are deriving clinical benefit may continue to receive protocol therapy beyond progression as long as they meet the following criteria:
 - Continue to meet treatment criteria
 - Investigator-assessed clinical benefit
 - Tolerance of study drug
 - Stable performance status
 - Treatment beyond progression will not delay an imminent intervention to prevent serious complications of disease progression (e.g., CNS metastases)
- *If the patient has IR per LYRIC criteria and is receiving therapy beyond progression:*
 - A confirmatory PET-CT should be performed within 12 weeks after initial progression to determine whether the patient meets PD criteria according to the LYRIC criteria¹⁰.
 - Further progression is defined according to the LYRIC criteria
 - Protocol therapy should be discontinued permanently upon documentation of PD per the LYRIC criteria
- Unacceptable toxicity despite dose delay/ modification

- **Note:** If one agent is delayed due to toxicity, then participants may continue with monotherapy for the other agent.
- Completed protocol therapy.
- General or specific changes in the participant's condition (including intercurrent illness) which render the participant unacceptable for further treatment in the judgment of the investigator
- Withdrawal of consent for further protocol therapy by the participant (See Section 16.5)

Once participants meet criteria for removal from protocol therapy, the participant should then proceed to End of Protocol Therapy assessments and follow-up.

Documentation of the reason for discontinuing protocol therapy and the date effective should be made in the medical record and appropriate eCRF. The COH DCC and the Study PI should be promptly notified of the change in participant status.

5.11 Follow-Up

Following completion of protocol therapy, all participants will enter follow-up after ending protocol treatment. This is comprised of:

- **Safety Follow-up-** 30 days post-last dose of protocol therapy through to (a) 90 days post-last dose of protocol therapy or (b) until initiation of a new anticancer therapy (whichever occurs sooner)
- Note: the period for safety follow-up will be extended until stabilization or resolution for all reportable AEs (per the agreement of the Study PI) and accompanying follow-up safety report.
- **Response Follow-up-** for those who have yet to have disease progression.
- **Survival Follow-up-** for those who progressed or completed Response Follow-up.

This follow-up will be performed typically via medical record review. It will entail (a) Disease status (for those who have yet to progress) (b) Vital status (all participants).

Assessment time points and windows are detailed in [Section 10.0](#).

5.12 Duration of Study Participation

Study participation may conclude when any of the following occur:

- Completion of study activities
- Withdrawal of consent (See Section 16.5)
- Participant is lost to follow-up. All attempts to contact the participant must be documented.
- At the discretion of the investigator for safety, behavioral, study termination or administrative reasons

Documentation of the reason for discontinuing study participation and the date effective should be made in the medical record and appropriate eCRF. The COH DCC should be promptly notified of the change in participant status.

5.13 Supportive Care, Prohibited Medications and Concomitant Therapy

Participants must be instructed not to take any additional medications (including over-the-counter products) during the trial without prior consultation with the investigator.

If concomitant therapy must be added or changed, including over-the-counter medications or alternative therapies, the reason and name of the agent/therapy should be recorded in the eCRF and the medical record.

5.13.1 Prohibited concomitant medication and medications to use with caution

The following are **prohibited** from Day 1 of protocol therapy until end of protocol therapy (last day of study agent or decision to end study agent(s) whichever occurs later):

- Antineoplastic systemic chemotherapy or biological therapy
- Immunotherapy not specified in this protocol
- Chemotherapy not specified in this protocol
- Other investigational agents other than pembrolizumab and pralatrexate
- Live vaccines
- Systemic glucocorticoids for any purpose other than to modulate symptoms from an event of clinical interest of suspected immunologic etiology. The use of physiologic doses of corticosteroids may be approved after consultation with the PI.

Participants who, in the assessment by the investigator, require the use of any of the aforementioned treatments for clinical management should be removed from the study.

The following medications should be **used with caution**:

- “Sulfa” antibiotics
- Non-steroidal anti-inflammatory drugs
- Probenecid

When administering pralatrexate to patients receiving probenecid or other drugs that may affect relevant transporter systems (eg, NSAIDs), monitor patients closely for signs of systemic toxicity due to increased drug exposure.

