7.7 Expedited Reporting

Table 7.7 indicates what events must be reported expeditiously.

Table 7.7 Criteria for Expedited Reporting

Time point	What to report expeditiously
From the signing of the consent to study completion	All unanticipated problems
From Screening until Day 1 of protocol therapy	
 • All SAEs related to protocol procedures • Pregnancy and lactation • Any reason for not starting Day 1 of protocol therapy
For the time period beginning at treatment through 90 days following cessation of treatment, or 30 days following cessation of treatment if the subject initiates new anticancer therapy, whichever is earlier	
 • All SAEs regardless of relationship to protocol therapy, study procedure, underlying disease or concomitant treatment. • Death due to any cause other than progression of the cancer under study. • All AEs that meet the definition of an unanticipated problem. • Overdose of either agent. • Pregnancies and lactation. • Abnormal liver function tests • Discontinuation of protocol therapy due to unusual or unusually severe AE considered related to protocol therapy
For participants yet to initiate anti-cancer therapy: From Day 1 of therapy up to 120 days post-last pembrolizumab dose	
 • Pregnancies and lactation.
Post Safety follow-up to removal from study	
 • All SAEs that are considered possibly, probably, or definitely related to pembrolizumab

NOTE: All events reported expeditiously require follow-up reporting until the event is resolved, stabilized, or

determined to be irreversible by the investigator.

The DCC should be consulted prior to ending the follow-up of events that have stabilized.

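### Section 5.13.1 takes patients who need a prohibited treatment off the study, which conflicts with the follow-up promised in 5.10–5.11 and, if applied literally, can cut short secondary-endpoint and late-safety data

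*Combined protocol and SAP*

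**What the plan says.** Section 5.13.1 lists treatments that are not allowed from Day 1 "until end of protocol therapy (last day of study agent or decision to end study agent(s) whichever occurs later". The list includes "Antineoplastic systemic chemotherapy or biological therapy", other immunotherapy, other investigational agents, live vaccines, and systemic glucocorticoids outside stated exceptions. Participants who in the investigator's assessment "require the use of any of the aforementioned treatments for clinical management should be removed from the study".

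Elsewhere the protocol treats leaving therapy and leaving the study as different events:

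- Section 5.10, on leaving therapy: "Once participants meet criteria for removal from protocol therapy, the participant should then proceed to End of Protocol Therapy assessments and follow-up".
- Section 5.11: "Following completion of protocol therapy, all participants will enter follow-up after ending protocol treatment". Disease status is then collected for patients who have not progressed, and vital status for all.
- Section 5.12, on ending participation, lists completion of study activities, withdrawal of consent, loss to follow-up, and investigator discretion for certain reasons. Need for a prohibited treatment is not named.
- Section 16.5 likewise separates stopping treatment from stopping procedures or data collection.

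**The concern.** Being off the study has consequences that being off therapy does not. Under footnote q of the Section 10 calendar, response follow-up ends at progression or when the patient goes off study. The last row of Table 7.7, headed "Post Safety follow-up to removal from study", ends late reporting of pembrolizumab-related SAEs at the same point. Section 11.2 censors PFS, DOR and OS at last follow-up and has no rule for removal or for new anticancer therapy.

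A patient who needs other systemic lymphoma treatment before progression is documented is plausibly doing badly. If follow-up stops then, censoring depends on prognosis, the Kaplan-Meier assumption of non-informative censoring fails, and PFS and OS look better than they are. A patient removed for a reason unrelated to prognosis, such as a live vaccine, adds little bias, but follow-up is still lost, including DOR information if the patient was responding.

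**Working it through.** The plan states no figure on this point, so the check is mainly a comparison of passages.

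**1. Which rule governs?** Need for a prohibited treatment is not itself a listed criterion in 5.10 or a listed reason in 5.12. Only 5.13.1 addresses it, and it uses the study-level term. Section 5.11 allows no exception to follow-up. Nothing says which passage prevails.

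**2. What could a literal reading end?**

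- Response follow-up: yes, through footnote q.
- Late pembrolizumab-related SAE reporting: yes, through the last row of Table 7.7.
- Survival status: possibly, although 5.11 collects vital status for all.
- The main all-SAE window in Table 7.7: not by its own terms. It runs from cessation of treatment, for 90 days, or 30 days if new anticancer therapy starts.

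**3. Who is exposed for PFS?** Only patients removed before documented progression. Section 11.1 places the first restaging in Cycle 4, and the calendar puts it at Days 15 to 21 of that cycle. Three 21-day cycles are 63 days, so it falls 63 + 15 = 78 to 63 + 21 = 84 days after the start, about 11 to 12 weeks (before visit windows and delays). Section 5.7 foresees patients stopping for progression before that scan and only encourages imaging to confirm it. The exposed group is therefore foreseeable.

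**4. Size.** The removal rate is not in the documents. Assume k = 1 to 4 of the 24 patients in the efficacy set.

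- Share of the set: 1/24 = 4.2%; 2/24 = 8.3%; 4/24 = 16.7%.
- Ceiling on the Kaplan-Meier error: with d true events by a given time and no other censoring, the true estimate is (24 − d)/24. If k of those events are censored instead, the estimate is at most (24 − d + k)/24. The difference is at most k/24, or 4 to 17 percentage points. For OS this requires that every such patient dies by that time and that no vital status is captured.
- Illustration for median PFS: assume exponential times, a true median of 3.5 months (the single-agent pralatrexate figure in 2.1.1, used only as a scale), and that all 24 patients would otherwise have an event. If a share f = k/24 of events is censored at removal, the apparent median is 3.5/(1 − f). For k = 1 this is 3.5/0.958 = 3.65 months; for k = 2, 3.5/0.917 = 3.82; for k = 4, 3.5/0.833 = 4.20.

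**5. What does not move?** ORR is defined on responses during study treatment. The 24-patient target and the stated standard error do not depend on later follow-up: √(0.3 × 0.7/24) = 9.4% and √(0.5 × 0.5/24) = 10.2%, as the plan says.

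**The case against.** The best defence is that 5.13.1 is loosely worded and the rest of the protocol shows what was meant.

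- Section 5.11 sends everyone to follow-up and collects vital status for all. Footnote q adds at least a year of response follow-up for patients who have not progressed. Footnote z moves those who end response follow-up into survival follow-up by record review, registry or telephone. The calendar also collects later anticancer therapy.
- Most patients who need urgent lymphoma treatment would be expected to meet the 5.10 progression criterion. Others may meet "General or specific changes in the participant's condition (including intercurrent illness) which render the participant unacceptable for further treatment". Both routes lead to follow-up, and the prohibition lapses once study agents have ended and the decision to end them has been made.
- Steroids for suspected immune-related events are exempt, and physiologic doses may be approved.
- Patients with documented progression already count as PFS events. PFS and OS are secondary estimates with no hypothesis test.

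All of this stands, and it limits the point. A reader might infer that patients needing urgent lymphoma treatment are lost to PFS, OS and safety follow-up, or that SAE collection stops for them. The documents do not support either. Losing OS requires a site to follow one sentence over several others, and only the last row of Table 7.7 ends at removal from the study. For patients starting new anticancer therapy, 5.11 ends safety follow-up then in any case, so 5.13.1 does not cause that loss.

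The defence does not remove the conflict. Evidence that continued follow-up was intended does not tell a site which instruction to follow. The 5.10 criteria also do not clearly cover a patient who is otherwise well but needs a live vaccine or a non-exempt steroid.

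**Conclusion.** The inconsistency is real and should be resolved. Read literally, 5.13.1 can end response follow-up, late pembrolizumab-related SAE reporting and possibly survival follow-up for patients removed before documented progression. The resulting censoring under 11.2 may be informative and would then bias PFS and OS upward.

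The size is uncertain. The 4 to 17 percentage points are a ceiling resting on an assumed 1 to 4 removals, literal application in every case, and an event for each of those patients. The apparent median of 3.65 to 4.20 months against 3.5 adds the exponential assumption. Neither is an expected effect. The point concerns the secondary time-to-event endpoints and late safety, and leaves the primary ORR and the design figures essentially untouched.

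**What to change.** Reconcile 5.13.1 with 5.10–5.12. One sentence would do: for participants who need a listed treatment, end-of-treatment assessments and safety, response and survival follow-up continue as described in 5.10 and 5.11, unless a reason in 5.12 ends their participation. This settles data collection only. It need not change which treatments are prohibited or when therapy stops.

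A companion line in 11.2 saying how PFS and DOR treat new anticancer therapy before documented progression would help, since no rule is given now.

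The cost is a short text change in an amendment. The assessments are already planned, and 5.11 expects follow-up to be done typically by record review. No sample size or design figure changes.
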